7.3 Variables

Each treatment/variable definition will be based on standard concepts in the OMOP Standardized Vocabularies. Variables will be identified using pre-specified concept sets reviewed by a core team of clinicians, epidemiologists, vocabulary experts, and health data scientists with extensive expertise in the use of the OMOP CDM and the OHDSI tools. Some of the codes used and validated before will be reused in this project.

7.3.1. COVID-19 diagnosis

The definitions used for COVID-19 diagnosis will depend on the data source, for example, the primary care data sources usually do not contain the laboratory values. All the analyses will be run on the main definition while the alternative definitions will be used for secondary objective 4 - to explore how COVID-19 is captured across different databases. (see Appendix 1 for code lists)

1. Catch-all (main definition, the most sensitive)

¹ Cardiovascular disease as a subgroup variable has a different definition from the composite cardiovascular event as an adverse event which is focused on acute and severe outcomes.

Defined either as the first confirmed diagnosis for COVID-19 **OR** the first SARS-CoV-2 positive PCR test, if both present the earliest date will be considered.

Alternative definitions

2. Diagnosis confirmed (diagCOVID-19)

Defined as one of the following medical codes for COVID-19 at any time (first occurrence considered):

- U07.1 COVID-19, virus identified
- U07.2 COVID-19, virus not identified

3. Laboratory confirmed (labCOVID-19)

Defined as a record of SARS-CoV-2 positive PCR as performed on nasopharyngeal swabs and/or on respiratory tract secretions and aspirates.

We will not include the testing for the presence of antibodies due to the issue of not knowing the point of infection via antibody testing. If patient has more than one test, first occurrence will be considered

4. Symptomatic COVID-19.

At least two symptoms of the following

- Cough
- Dyspnoea
- Fever, unspecified
- Malaise and fatigue
- Myalgia
- Anosmia, Hyposmia or Dysgeusia episodes

5. Suspected COVID-19

- Coronavirus as the cause of diseases classified to other chapters
- Coronavirus infection, unspecified site
- Other viral pneumonia
- Acute bronchitis due to other specified organisms
- Unspecified acute lower respiratory infection
- Bronchitis, not specified as acute or chronic
- Adult respiratory distress syndrome
- Other specified respiratory disorders
- Special screening examination for other viral diseases
- Contact with and exposure to other communicable diseases

This classification is aligned with the ICD-10 International coding guidance on COVID-19 disease (20)

7.3.2 Exposures

The following exposures of interest are captured in this study

Table 2 Exposures of interest

	Cohort	When is measured
Glucocorticoids used in COVID-19 indication	All	At diagnosis index date and follow-up
Glucocorticoids for pre-existing conditions	Only in prevalent users' cohort	Before diagnosis index date
Other COVID-19 treatments: 
 • antiviral therapy (AV) • antibiotic therapy (AB) • immune-based therapy (IB) • antithrombotic therapy (AT) • anti-hypertensives (AH) • statins (S) • anti-diabetic (AD) (see Appendix 3)	All	At diagnosis index date and during follow-up
Oxygen therapies	All	At diagnosis index date and during follow-up*

* During follow-up this will be considered as an outcome

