7.2.3 Follow-up

Two index date definitions will be applied as appropriate for each objective.

- Diagnosis index date is defined as a positive PCR test for SARS-CoV-2 (labCOVID-19) or a confirmed COVID-19 diagnosis(diagCOVID-19) whichever is the earliest.
- Treatment index date is defined as start of first systemic glucocorticoid treatment episode specifically for the treatment of COVID-19, irrespective of whether the patient is a prevalent or naïve user.

Follow up for all patients will begin from the index date until they experience the outcome of interest (endpoint, depending on the objective) or until cohort exit (date of censoring). The patients will be followed up for maximum 90 days or until censoring occurs, censoring criteria are:

- death
- patient exit (deregister) from a contributing data provider (GP practice)
- end of the database's data collection
- end of study period (latest data cut-off)

The lookback window for evaluating risk factors, medical history is 365 days and will be applied only to outpatient cohorts.

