Steroids often have adjusted dose regimens such that drug may be slowly increased or decreased over time and short acute treatment episodes are also possible. Such changes in dose over time will not be examined, however total cumulative dose will be examined in relation to outcomes of interest (see below).

Cumulative dose

For glucocorticoids used in COVID-19 indication, orally administered, if quantity is available, the formula to calculate the cumulative exposure in mg is described below:

$$Cumulative\ dose_{solid}[mg] = \sum_{all\ exposures} quantity \times amount_value [mg]$$

If the **quantity is missing**, the number of units per day for solid formulations are extracted. The cumulative exposure in mg can then be calculated using the following formula:

$$Cumulative\ dose_{solid}[mg] = \sum_{exposures} units\ per\ day \times amount_value [mg] \times duration$$

For intravenous administration (bolus administration), the dose administered each time will be counted.

$$Cumulative\ dose\ intravenous [mg] = \sum_{all\ exposures} amount_value [mg]$$

Exposure groups for incidence calculation (secondary objective 2 and 3)

For the incidence rates calculation, an on-treatment exposure will be considered with mutually exclusive groups to allow calculation of incidence rates.

Each person will be classified as belonging to one of the following mutually exclusive exposure groups at treatment index date following COVID-19 diagnosis:

- Use of systemic glucocorticoids without other treatments for COVID-19 (drug and respiratory support)
- Use of systemic glucocorticoids plus other treatments for COVID-19 (drug and respiratory support)
- Only other treatments and respiratory support with no systemic glucocorticoids

- No specific treatments for COVID-19 infection (other concomitant treatments for indications other than for COVID-19 are allowed)

A single prescription would be enough to consider the patient as exposed. See section 7.3.2.1 for description of 'other treatment for COVID-19' that are included.

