Only the first episode of exposure will be considered, patients being censored when they switch to another treatment (including switch to another glucocorticoid) or when follow up ends. Duration of follow-up for each treatment cohort will be summarized and will constitute the denominator for calculation of effect estimates. A persistence window of 7 days between drug utilization records for each study drug will be allowed considered as continuous exposure for the outcome's assessment.

In case that more than 70% of the patients are censored, a sensitivity approach will be applied for objectives 2 and 3 (see Section 7.7.8).

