7.3.4 Disease severity outcomes

In ambulatory care cohorts

- Hospital admission
- Venous thromboembolism (VTE) or pulmonary embolism (PE)
- Disseminated intravascular coagulation (DIC)
- Death of any cause

In hospitalized cohorts

- Intensive services as an outcome in inpatient cohorts (including mechanical ventilation and Extracorporeal membrane oxygenation (ECMO))
- Discharge from hospital
- Death of any cause
- Venous thromboembolism (VTE) or pulmonary embolism (PE)
- Disseminated intravascular coagulation (DIC)

They will all be treated as time to event outcomes, see section 7.7 for details.

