7.3.5 Other Variables

Age – measured both as continuous and categorical variable in years. The following categories will be created:

- <18
- ≥18 and <65
- ≥ 65 and <75
- ≥75

Sex

- Male
- Female

Index month of diagnosis

Comorbidities

- Hypertension
- Type 2 diabetes mellitus
- Chronic obstructive pulmonary disease (COPD)
- Asthma
- Chronic kidney disease
- Ischemic stroke or haemorrhagic stroke
- Heart failure
- Acute myocardial infarction
- Arrhythmia

- Venous thromboembolism (VTE) or pulmonary embolism (PE)
- Obesity (using diagnosis codes)
- Smoker
- Alcohol/Drug abuse
- Autoimmune conditions (type 1 diabetes mellitus, rheumatoid arthritis, psoriasis, psoriatic arthritis, multiple sclerosis, systemic lupus erythematosus, Addisons, Graves, Sjogrens, Hashimoto, myasthenia gravis, autoimmune vasculitis, pernicious anaemia, celiac disease, scleroderma, sarcoid, ulcerative colitis, Crohn disease)
- Organ transplantation,
- Cancer
- Dementia,
- Major psychiatric disorder

These will be used to describe the cohorts at relevant index dates(s) and some of these will be selected as risk factors/confounders for the incidence rates analysis, see section 7.7 for details.

Respiratory support

Patients will be considered having adjunctive respiratory support if available medical records data are available for the following interventions on or post COVID-19 diagnosis:

- Any type of respiratory support
- Invasive mechanical ventilation (including ECMO)
- ECMO only

If no records are observed, then the patient will be considered as receiving no respiratory support.

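### Respiratory support both defines the treatment groups and, as ventilation or ECMO, is a hospital outcome, with no consistent date separating the two roles

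*Protocol*

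**What the plan says.** **Exposure role.** Section 7.3.2.3 of the protocol, repeated in 7.7.4, forms four groups for the incidence rates of secondary objectives 2 and 3:

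1. "Use of systemic glucocorticoids without other treatments for COVID-19 (drug and respiratory support";
2. glucocorticoids together with such treatments;
3. "Only other treatments and respiratory support with no systemic glucocorticoids";
4. no treatment aimed at COVID-19.

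Section 7.3.2.3 describes these as "mutually exclusive exposure groups at treatment index date following COVID-19 diagnosis".

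**Outcome role.** Section 7.3.4 lists for the hospitalized cohorts "Intensive services as an outcome in inpatient cohorts (including mechanical ventilation and Extracorporeal membrane oxygenation (ECMO". In Table 2 (7.3.2), a footnote to the oxygen-therapy row reads "During follow-up this will be considered as an outcome".

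**Dates.**
- Section 7.2.3: "Treatment index date is defined as start of first systemic glucocorticoid treatment episode specifically for the treatment of COVID-19".
- Section 7.3.5: "Patients will be considered having adjunctive respiratory support if available medical records data are available for the following interventions on or post COVID-19 diagnosis". No end to that window is given.

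**Censoring.** Section 7.3.2.3 considers only the first exposure episode, "patients being censored when they switch to another treatment (including switch to another glucocorticoid". Section 7.7.4 says the same.

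**The concern.** If a ventilation record made during follow-up can decide which group a patient belongs to, patients are grouped by the outcome itself. A ventilated patient can then never be counted in a group defined by the absence of respiratory support. A similar result arises if starting ventilation is treated as a change of treatment and follow-up is cut before the event is counted.

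In either case the zero rates in groups 1 and 4 would come from the definitions and say nothing about the patients. Under the first mechanism the rates in groups 2 and 3 would also be too high. Section 7.5 reports only one database with hospitalized patients, around 2,000, so no second source would reveal the artefact. Two programmers could each follow the text and produce opposite patterns.

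**Working it through.** The plan states no figure for this outcome by group, so there is nothing to reproduce. Three checks were made.

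**1. Are exposure and outcome the same records?** Appendix 1, list 4.3 (intensive services, the outcome) has 30 concepts. List 6.2 (invasive respiratory support) has 29. They share 28. Only two visit concepts (262 and 9201) are unique to 4.3, and only one tracheostomy-device removal concept (2743216) is unique to 6.2. Appendix 1 calls its lists examples, but as written the ventilation, ECMO and tracheostomy records that mark the exposure are those that mark the event. Plain oxygen therapy (list 6.1) is not in 4.3, so oxygen can allocate a patient without being this outcome.

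**2. Does any date rule separate the roles?**
- 7.3.2.3 places classification at treatment index. Under 7.3.2.1 that falls between 2 days before and 30 days after diagnosis.
- Table 2 measures respiratory support at the diagnosis index and in follow-up.
- 7.3.5 counts support from diagnosis onward, with no upper limit and no link to treatment index.
- 7.2.3 defines treatment index by the glucocorticoid start. Groups 3 and 4 have none, and 7.7.4 refers only to a relevant index date. These two groups have no stated time zero.
- 7.2.2.1 excludes hospital patients with intensive services in the 30 days before or on index, in context the diagnosis index. Invasive support that allocates such a patient must therefore start after diagnosis, when it can also be the outcome.

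**3. What does each reading do to the reported risk?** Assumptions, for illustration only: N = 2,000; the same true 30-day risk v in every group; group shares s1 to s4.

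*Reading A: the 7.3.5 window allocates.* Patients ventilated in group 1 move to group 2, and those in group 4 move to group 3.
- Groups 1 and 4: no events remain, so the risk is 0.
- Group 2: (s2·v + s1·v) / (s2 + s1·v). Group 3 is the same with s3 and s4.
- Equal shares, v = 10%: 500 per group and 50 events in each. Group 1 becomes 0/450. Group 2 becomes (50 + 50)/(500 + 50) = 100/550 = 18.2%.
- Shares 10/40/40/10, v = 10%: group 2 becomes (80 + 20)/(800 + 20) = 100/820 = 12.2%.

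*Reading B: groups fixed at index; starting support is a switch and censors before the event counts.* Groups 1 and 4 show 0. Groups 2 and 3 show v, if starting support there is not a switch because those groups already include it.

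*Reading C: groups fixed at index; later support is only an event.* All four groups show v.

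Reported risk in groups 1/2/3/4:

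| v | A, equal shares | A, 10/40/40/10 | B | C |
|---|---|---|---|---|
| 5% | 0/9.5/9.5/0% | 0/6.2/6.2/0% | 0/5/5/0% | 5% in all |
| 10% | 0/18.2/18.2/0% | 0/12.2/12.2/0% | 0/10/10/0% | 10% in all |
| 20% | 0/33.3/33.3/0% | 0/23.8/23.8/0% | 0/20/20/0% | 20% in all |

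The zeros do not depend on v or on the shares. They concern events recorded through the 28 shared concepts.

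**The case against.** The best defence is that the protocol already separates the roles. Classification is at treatment index and the Table 2 footnote makes later support an outcome; together these give Reading C, with no artefact. Section 7.3.5 sits under other variables and need not be an allocation rule: the primary objective describes respiratory support during follow-up, which needs an open window. No sentence says that starting ventilation is a switch, and adding it to a continuing glucocorticoid is not obviously one. Even with both on the same day, 7.2.3 makes death both a censoring criterion and, through 7.3.4, an outcome, so the protocol evidently means to count an event on a censoring date. A tie rule can be left to the SAP. Comparison between treatments is out of scope, and 7.9.1 admits that on-treatment classification may miss deterioration.

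Much of this stands. A reader might infer that the outcome is fixed by construction whatever the reading, that the plan orders censoring at the start of ventilation, or that all ventilated patients must end up in groups 2 and 3. The documents support none of these. Reading C is available, the switch is only an inference from the wording that places respiratory support among other treatments, and under Reading B patients stay in the group they were first given.

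The defence still does not close the gap. The footnote belongs to the oxygen row and to the diagnosis index. The classification date does not exist for groups 3 and 4. The only section saying when a patient counts as having respiratory support sets no end date. The 7.9.1 caveat does not address the overlap. The intention-to-treat analysis in 7.7.8 runs only if more than 70% are censored by switching, and it would not undo allocation based on later support.

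**Conclusion.** The concern holds in a conditional form. Respiratory support is both a group-defining exposure and, as ventilation or ECMO, a hospital outcome on nearly identical codes, without a consistent cut-off date. Under two of three readings (A and B), ventilation or ECMO events become impossible in groups 1 and 4. In groups 2 and 3 the risk is inflated (A) or unchanged (B), not fixed. Under the third (C) there is no artefact, but the protocol does not state that reading consistently.

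The size of the inflation rests on the assumed common risk and group shares; the zeros do not. This is more than detail left for the SAP, because applying the window that 7.3.5 states would allocate patients on the outcome. The reach is limited: it is one of five hospital outcomes in 7.3.4, none named as the main one, under secondary objective 3 and in one of eight databases. It should be fixed before the analysis is run.

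**What to change.** In 7.3.2.3 and 7.3.5 of the protocol:

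- define a time zero for all four groups, including the two without glucocorticoids;
- count respiratory support for group allocation only if recorded from diagnosis up to and including that date, and keep the open window of 7.3.5 for description only;
- state that support starting after time zero is an outcome event and not a censoring switch, and that an event is counted before any censoring on the same day;
- exclude patients already receiving an intensive service at time zero from the risk set for that outcome, because 7.2.2.1 removes them only up to what is, in context, the diagnosis index.

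The cost is a few sentences, matching wording in 7.7.4 and Table 2, and a date condition in the cohort code. No new data are needed. Under the illustration above, the assumed risk is then recovered in all four groups.

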7.3.2.1 Glucocorticoids

Glucocorticoids used in COVID-19 indication

The primary treatment group of interest is based on exposure to systemic glucocorticoids. The following drugs will be considered as being used for COVID-19 diagnosis:

- Dexamethasone (H02AB02)
- Prednisone (H02AB07)
- Prednisolone (H02AB06)
- Methylprednisolone (H02AB04)
- Hydrocortisone (H02AB09)

Only glucocorticoids which were investigated in clinical trials (13,21) or are recommended by clinical guidelines are included (22–24) to avoid misclassification of steroids used for other conditions. As indication is not captured in the available databases, a glucocorticoid treatment will be considered to have been initiated for COVID-19 treatment if:

For incident users

- The glucocorticoid treatment was initiated between 2 before and 30 days after COVID-19 diagnosis date (21)
- It is one of the five glucocorticoids recommended for COVID-19 as above

For prevalent users

- The glucocorticoid treatment was initiated between 2 before and 30 days after COVID-19 diagnosis date
- It is one of the five glucocorticoids recommended for COVID-19 as above
- The glucocorticoid started after COVID-19 diagnosis differs from the chronically used glucocorticoids OR there is a change in dose or schedule of administration compared to the prevalent use, occurred after COVID-19 diagnosis.

Glucocorticoids for pre-existing conditions

For the prevalent users, any steroid in the ATC class H02 glucocorticoids for systemic use will be considered. A patient is defined as a systemic glucocorticoids prevalent user if it has at least one prior exposure to systemic² glucocorticoids in the 120 days prior to diagnosis index date.

For the description of prevalent users of glucocorticoids, categories of use will be created based on proportion of days covered (PDC) during the lookback period. PDC is calculated as the number of days in period covered by prescriptions divided by number of days in the period.

- PDC > 85% as heavy user
- PDC 50-85% as moderate user
- less than 50% PDC as light user

Another categorization of prevalent glucocorticoids user will be based on how recently in the past the last prescription was observed:

- current use (concomitant on date of COVID-19 diagnosis)
- recent use (between 15-30 days before date of COVID-19 diagnosis)
- remote use (use ended more than 30 days before date of COVID-19 diagnosis)

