7.2.4 Subgroups

The following subgroups will be used to stratify the descriptive tables in Primary objective 1 and secondary objective 1-3. These are a mix of contraindications (e.g. heart failure, myocardial infarction, ischaemic stroke, hypertension, diabetes) and underrepresented groups in clinical trials (e.g. renal

impairment, hepatic impairment) as well as conditions for which glucocorticoids are indicated (COPD and asthma).

Comorbidities

- Cardiovascular diseases¹ (e.g., hypertension, arrhythmia, valve disorders, stroke, acute myocardial infarction)
- Type 2 diabetes mellitus
- Respiratory diseases: asthma, COPD
- Renal impairment
- Hepatic impairment
- Autoimmune diseases (e.g., type 1 diabetes mellitus, rheumatoid arthritis, psoriasis, psoriatic arthritis, multiple sclerosis, systemic lupus erythematosus, Addison's, Graves, Sjogrens, Hashimoto, myasthenia gravis, autoimmune vasculitis, pernicious anaemia, celiac disease, scleroderma, sarcoid, ulcerative colitis, Crohn disease)
- Starting dose of steroids: low dose and high dose (the threshold will be decided based on data distribution)

Speciality of the healthcare practitioner (GPs vs specialists) in databases that record this information

The subgroups are not mutually exclusive, and patients can contribute to more than one subgroup, The above subgroups will be used for descriptive purposes and will not be used for statistical comparisons.

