LPD Italy is comprised of anonymised patient records collected from software used by GPs during an office visit to document patients' clinical records. Data coverage includes over 2M patient records with at least one visit and 119.5M prescription orders across 900 GP practices. Dates of service include from 2004 through present. Observation time is defined by the first and last consultation dates. Drugs are captured as prescription records with product, quantity, dosing directions, strength, indication and date of consultation.

Integrated Primary Care Information (IPCI), The Netherlands

IPCI is collected from EHR records of patients registered with their GPs throughout the Netherlands. The selection of 391 GPs is representative of the entire country. The database contains records from 2.6 million patients out of a Dutch population of 17M (8.2%) starting in 1996. The median follow-up is 2.2 years. The observation period for a patient is determined by the date of registration at the GP and the date of leave/death. The observation period start date is refined by many quality indicators, e.g. exclusion of peaks of conditions when registering at the GP. All data before the observation period is kept as history data. Drugs are captured as prescription records with product, quantity, dosing directions, strength and indication. Drugs not prescribed in the GP setting might be underreported. Indications are available as diagnoses by the GPs and, indirectly, from secondary care providers but the latter might not be complete. Approval needs to be obtained for each study from the Governance Board. (5) The IPCI database is currently increasing the update frequency because of the COVID-19 pandemic (now updated till March 2020).

Information System for Research in Primary Care (SIDIAP), IDIAP Jordi Gol (Spain)

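### The COVID-19 glucocorticoid proxy rests on the statement that indication is not captured, but section 7.4 lists indication as a prescription field in LPD Italy and IPCI, and the plan never uses it

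*Protocol*

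**What the plan says.** Section 7.3.2.1 gives the reason for the attribution rule: "As indication is not captured in the available databases, a glucocorticoid treatment will be considered to have been initiated for COVID-19 treatment if" certain conditions are met. Two conditions apply to everyone: "The glucocorticoid treatment was initiated between 2 before and 30 days after COVID-19 diagnosis date" and "It is one of the five glucocorticoids recommended for COVID-19 as above". Prevalent users face a third: "The glucocorticoid started after COVID-19 diagnosis differs from the chronically used glucocorticoids OR there is a change in dose or schedule of administration", compared with their earlier use. No condition refers to a recorded indication.

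Section 7.4 describes the sources. For LPD Italy: "Drugs are captured as prescription records with product, quantity, dosing directions, strength, indication and date of consultation". For IPCI: "Drugs are captured as prescription records with product, quantity, dosing directions, strength and indication", and further: "Indications are available as diagnoses by the GPs and, indirectly, from secondary care providers but the latter might not be complete".

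The rule carries much of the study. The primary objective (section 6.2) is steroid use for the treatment of COVID-19. The treatment index date (section 7.2.3) is the start of the first episode given for that purpose. The exposure groups for secondary objectives 2 and 3 (section 7.3.2.3) are assigned from it.

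**The concern.** The blanket premise in section 7.3.2.1 and the field lists in section 7.4 cannot both be right as worded. If section 7.4 is right, the plan infers the reason for treatment in two databases that record it, and can class as COVID-19 treatment a course whose own record gives a different reason.

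The protocol sees the risk: section 7.3.2.1 restricts the list to five substances so that steroids given for other diseases are not swept in. The restriction helps only in part, because the list includes prednisolone and prednisone, and section 7.2.4 selects among its subgroups "conditions for which glucocorticoids are indicated (COPD and asthma"). A course for an asthma or COPD flare can therefore meet the proxy.

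At stake in the Italian and Dutch results are the reported amount of COVID-19 steroid use, time to initiation, starting dose and duration. The make-up of the exposure groups is also affected. Those groups are mutually exclusive, so a misattributed patient is both added to a steroid group and removed from a non-steroid group.

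**Working it through.** The plan gives no figure to reproduce, so the check sets the sections side by side.

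**Step 1. Which databases list indication as a drug-record field (section 7.4)?**

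| Database | What section 7.4 says about drug records | Indication listed? |
|---|---|---|
| LPD Belgium | GP prescriptions | No |
| LPD France | GP prescriptions | No |
| DA Germany | Prescriptions of marketed products | No |
| IMRD UK | Prescriptions | No |
| LPD Italy | Prescription records with several fields | Yes |
| IPCI | Prescription records with several fields | Yes, secondary-care part possibly incomplete |
| SIDIAP | Prescriptions and pharmacy dispensing | No |
| HM Hospitales | Medicines dispensed in hospital | No |

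The count is 2 of 8 databases, or 2 of the 7 ambulatory ones, against the 0 of 8 that section 7.3.2.1 implies.

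**Step 2. How wide is the window?** Two days before diagnosis, the day itself and 30 days after: 2 + 1 + 30 = 33 calendar days.

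**Step 3. Apply the rule to a hypothetical naive user.** Take a patient in LPD Italy with no steroid in the 120 days before diagnosis, and a prednisolone prescription on day +20 recorded for asthma.
- Window: -2 ≤ 20 ≤ 30, so the condition is met.
- Substance: prednisolone is on the list, so the condition is met.
- No further condition applies to naive users.

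The patient is classed as treated for COVID-19 and receives a treatment index date of day +20. The start counts as an event in the Kaplan-Meier analysis of time to initiation (section 7.7.2), and the patient enters a steroid exposure group. The recorded indication is never consulted.

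**Step 4. Apply it to a prevalent user.** An unchanged refill of the chronic steroid fails the third condition and is not counted. A flare treated with a different listed substance, or a listed one at a changed dose or schedule, passes. The problem is weaker here but remains.

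**Step 5. Is it handled elsewhere?** Section 7.7.8 has sensitivity analyses on the reference group, on earlier short-term steroid use and on an intention-to-treat approach. Section 7.9 covers misclassified COVID-19 diagnosis, confounding by indication and severity, under-recorded hospital exposure and wrong naive status. None uses recorded indication or mentions steroid courses attributed to the wrong disease. The ENCePP checklist (Appendix 2, item 5.2) answers No on validity of the exposure measurement.

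**Step 6. Can it be sized?** No. Section 7.5 gives only a per-database range of COVID-19 patients and a total. The protocol has no count of steroid starts by database, no share of prescriptions with a recorded indication, and no background rate of starts for other reasons.

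**The case against.** The best defence is that the sentence may be true of the data actually analysed. Section 7.2 says the study runs on data mapped to the OMOP common data model, and section 7.3 builds every variable from OMOP standard concepts. Section 7.4 describes the source databases. Nothing says that the link from a prescription to its indication survives the mapping, and in IPCI the indications are described as diagnoses, which may not all be tied to a prescription. This stands as a limit: usability of the field is not shown. It does not rescue the wording, because the protocol gives absence of capture as its reason, not loss in mapping.

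Second, one common rule is a defensible choice for a multi-database study that plans a meta-analysis (section 7.7.7). A reader might infer that recorded indication should replace the proxy as the main definition in the two databases. The documents do not support going that far. A course given for COVID-19 may be recorded under pre-existing asthma or COPD, so strict exclusion would trade false positives for false negatives and make the definition differ between countries.

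Third, a reader might take the proxy for a bare day window, or think recorded indication the only way to check it. Neither is right. The drug list and the prevalent-user condition also filter. Sections 7.2.4 and 7.7.2 already plan tables by asthma, COPD and autoimmune disease, together with the distribution of time to initiation. Those are indirect checks; the recorded indication would be a direct one.

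Finally, operational detail may sit in the SAP, which is not at hand. The incorrect premise, however, is in the protocol.

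**Conclusion.** The point holds as an internal contradiction with a bounded consequence. The stated ground for the primary exposure definition is wrong for two of the eight databases, taking section 7.4 at its word. In those two, the rule counts courses recorded for another disease as COVID-19 treatment, most directly in naive users.

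A reader might want to attach a percentage to this. Any such figure would need assumed rates of steroid starts for COVID-19 and for other reasons, and the protocol supplies neither. The size is unknown and may be small. The direct effect is confined to the LPD Italy and IPCI results, which section 7.7 presents separately, and to any pooled estimate in which they take part.

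The conclusion assumes that section 7.4 describes the fields correctly and that at least part of the indication information can be used in the mapped data. If the second assumption fails, the misattribution cannot be checked this way, and what remains is a sentence to correct and a limitation to state.

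**What to change.** 1. Correct the sentence in section 7.3.2.1 so that it agrees with section 7.4: say which databases record indication, how complete it is, and whether it is available after mapping.
2. Keep the present proxy as the main definition in all databases.
3. In LPD Italy and IPCI, where the field is usable, tabulate the recorded indication of proxy-defined starts as COVID-19 or respiratory infection, asthma or COPD, other, and missing. This checks the proxy directly and helps in reading the other six databases.
4. In the same two databases, add to section 7.7.8 a sensitivity analysis of the primary tables that leaves out starts whose recorded indication is clearly unrelated to COVID-19. Keep starts with a blank or respiratory indication.
5. If the field does not survive the OMOP mapping, say so in section 7.3.2.1 and add the misattribution of steroid courses to section 7.9.

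The cost is a little extra analysis in two databases. The field may be incomplete, so the table should show the missing share and the sensitivity analysis should be read alongside it. The common definition, and so comparability between databases, is unchanged.
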